4.3. Dosing Frequency

In Part A, patients will receive a single IV infusion of KAN-101 on D1.

In Part B, patients will receive a total of 3 IV infusions of either KAN-101 or PBO (double-blind). A single IV infusion will be administered on D1, D4, and D7.

4.4. Blinding

Part A is open label.

Part B is double-blinded, such that study personnel (eg, Investigators, site coordinators) and patients are blinded to treatment assignments and will remain blinded throughout the study.

Unblinded personnel include those involved in drug preparation and allocation (eg, data systems support and pharmacists), and the study pharmacokineticist to allow for expedited review of PK data prior to SMC review.

The data for dose escalation in Part B will be presented and reviewed by the SMC in a blinded fashion.

After completion of SMC review and once all patients in the cohort have completed the study, the sponsor study team members involved in biomarker data analysis may be unblinded to complete pharmacodynamic assessments.

In the event of a medical emergency, the site may be unblinded if knowledge of the study treatment is necessary in order to provide appropriate urgent medical care.

4.5. Monitoring of Adverse Events

Patients will be monitored continuously for AEs while on study. AE severity will be assessed using the NCI CTCAE v5.0 or higher ([Appendix 1](#)).

4.6. Dose-Limiting Toxicities

Dose-limiting toxicities (DLTs) for Study KAN-101-01 include any \geq Grade 3 AE assessed as related to KAN-101 or Grade 2 AE assessed as related to KAN-101 not resolving within 14 days; DLTs do not include those AEs attributable solely to intercurrent illness or other concomitant medications. Any DLT experienced during the study will result in study pause and review by the SMC. Any \geq Grade 4 AE will result in notification of the FDA in parallel with the SMC and study dosing and enrollment will be paused pending review by FDA.

4.7. Dose Escalation Safety Period

In Part A, the dose escalation safety monitoring period is from the beginning of IV administration through D8. Any AEs that meet the above criteria but occur after the dose escalation safety monitoring period of Part A may be considered by the SMC in the evaluation for Part B dose selection.

The dose escalation safety monitoring period in Part B is from the beginning of the first IV administration of KAN-101/PBO through the D15 clinic visit, prior to initiating the GC.

The length of the monitoring periods for safety review is supported by nonclinical exposure data, suggesting KAN-101 will have cleared 5 half-lives, and nonclinical animal model data demonstrating that the tolerance induction mechanism can develop within 1 week of dosing. AEs and any abnormal clinical parameters, including laboratory findings, observed during this period will be used by the SMC to determine whether dose escalation should proceed.

No patient with a DLT will be replaced.

In both parts, patients will be monitored in the clinic for 10 hours following the first IV administration of KAN-101/PBO. In Part B, patients will be monitored in the clinic for 4 hours following completion of their second and third dose.

4.8. Safety Monitoring Committee

This study will utilize an SMC that will meet regularly to review all accumulated and available data, including safety and PK. The SMC will be comprised of three independent medical reviewers, including at least 1 CeD medical expert, as voting members. Non-voting members will include the study medical monitor, a medical representative from the Sponsor and other relevant study and site staff as required to address study conduct. The SMC will recommend all dose escalation decisions, and/or any recommended changes to the dosing paradigm based on review of the received data. The SMC will also make recommendations about the dose(s) selected for Part B.

4.9. Individual and Cohort Stopping Rules

During the dose escalation safety monitoring period, any DLT will result in a pause in enrollment and a thorough review by the SMC prior to treating any additional patients. Any \geq Grade 4 AE will result in notification of the FDA in parallel with the SMC and study dosing and enrollment will be paused pending review by FDA.

For Part A, if 1 of the first 3 patients experiences a DLT in a given cohort, 3 additional patients will be enrolled and evaluated in that cohort before dose escalation can occur if recommended by the SMC and only after consultation with the FDA for any \geq Grade 4 AE. If 2 or more patients experience a DLT at a given dose level during the dose escalation evaluation period of Part A, then that dose level will be considered a non-tolerated dose (NTD), and no further escalation will proceed.

If a patient experiences a DLT during the dose escalation safety monitoring period of Part B, no additional doses will be administered to that patient. If 1 patient experiences a DLT during the dose escalation safety monitoring period of Part B, the study will be paused to determine if any dose adjustments are needed and/or if the study should dose any additional patients. For any \geq Grade 4 AE the study would only continue after consultation with the FDA. If 2 or more patients experience a DLT during the dose escalation safety monitoring period of Part B, then that dose level will be considered an NTD, and no further escalation will proceed.

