10.5. Infusion-Related Reactions

If an IRR occurs during KAN-101 administration, the following treatment recommendations are provided and may be modified per local treatment standards and guidelines as appropriate.

- Grade 1 (mild): Infusion rate modification not indicated. Administer symptomatic treatment (eg, antihistamines, antipyretics, antiemetics) as needed. Closely monitor patient until resolution. Prophylaxis with diphenhydramine 50 mg (or equivalent) and/or acetaminophen/paracetamol 325 to 1000 mg is recommended at least 30 min prior to future KAN-101 infusions
- Grade 2 (moderate): Slow infusion to $\leq 50\%$ of the original infusion rate and treat symptoms with appropriate medical therapy, including but not limited to antihistamines, antipyretics, and analgesics. Increase monitoring of vital signs as medically indicated until patient is deemed stable. Prophylaxis with diphenhydramine 50 mg (or equivalent) and/or acetaminophen/paracetamol 325 to 1000 mg is recommended at least 30 min prior to future KAN-101 infusions
- Grade 3 (severe): Stop infusion and institute appropriate symptom-directed therapy, including but not limited to antihistamines, antipyretics, corticosteroids, bronchodilators, and O₂. Increase monitoring of vital signs as medically indicated until patient is deemed stable. If the reaction has not resolved within 6 hours, the remainder of the infusion will not be administered and KAN-101 will be permanently discontinued. Following the completion or termination of a restarted infusion due to an IRR, all patients must be monitored until resolution of symptoms or for 2 hours in the absence of additional symptoms. Prophylaxis with diphenhydramine 50 mg (or equivalent) and/or acetaminophen/paracetamol 325 to 1000 mg is required at least 30 min prior to future KAN-101 infusions. The next infusion should initiate at a rate of 2 hours per dose, or 50% of the rate at which the reaction occurred. If no IRRs are observed within the first 30 minutes, the infusion rate may increase to the 1-hour-per-dose rate as outlined in [Section 10.2](#). Permanently discontinue KAN-101 upon a second occurrence of a Grade 3 or greater infusion reaction.

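### In Part B, Section 4.9 bars further doses after a related Grade 3 infusion reaction, but Section 10.5 sets terms for the next infusion if the reaction resolves within 6 hours

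*Protocol*

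**What the plan says.** **DLT definition (Protocol 4.6).** A DLT is a "Grade 3 AE assessed as related to KAN-101 or Grade 2 AE assessed as related to KAN-101 not resolving within 14 days", where the first limb reads Grade 3 or higher. The only exclusion is for events due solely to intercurrent illness or other concomitant medication. Infusion reactions are not excluded, and neither are events that resolve quickly.

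**Window (Protocol 4.7).** In Part B the escalation safety period runs "from the beginning of the first IV administration of KAN-101/PBO through the D15 clinic visit", before the gluten challenge starts. It covers all three dosing days: D1, D4 and D7.

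**Patient-level stopping rule (Protocol 4.9).** "If a patient experiences a DLT during the dose escalation safety monitoring period of Part B, no additional doses will be administered" to that patient. No exception is given.

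**Study-level rule (Protocol 4.6).** "Any DLT experienced during the study will result in study pause and review by the SMC".

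**Infusion-reaction guidance (Protocol 10.5, Grade 3).** The infusion is stopped and the symptoms treated. "If the reaction has not resolved within 6 hours, the remainder of the infusion will not be administered and KAN-101 will be permanently discontinued". For other Grade 3 reactions, diphenhydramine and/or acetaminophen "is required at least 30 min prior to future KAN-101 infusions", a reduced starting rate is given for the next infusion, and permanent discontinuation follows a second reaction of Grade 3 or above. Section 10.2 also allows a longer infusion after a Grade 3 reaction and refers only to Section 10.5.

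**SAP 3.1** states that individual and cohort stopping rules follow Protocol Section 4.9.

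**The concern.** Two operative sections of the protocol give different answers about the same patient, and neither mentions the other. Site staff managing an infusion reaction will naturally turn to Section 10.5. There they find dosing instructions for the next visit and no statement that the event may already have ended that patient's treatment.

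What is at stake is patient safety in a first-in-human study. Doses are three days apart, so a patient with a severe drug-related reaction on D1 could be infused again on D4, or after a D4 reaction on D7, although Section 4.9 is written to prevent exactly that.

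**Working it through.** The plan gives no figure to reproduce. The check sets the rules side by side for one scenario and then counts where it can arise.

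**Scenario:** Part B, first Grade 3 infusion reaction, assessed as related, resolved within 6 hours.

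1. *Is it a DLT?* Yes, under 4.6. Section 11.2.2 counts Possible, Probable and Definite as drug related; only None and Remote are not.
2. *Is it inside the window?* Yes on every dosing day, under 4.7.
3. *What do the two sections provide next?*

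| Day of reaction | Scheduled doses left | Allowed by 4.9 | Described by 10.5 |
|---|---|---|---|
| D1 | 2 (D4, D7) | 0 | next infusion, premedicated and slowed |
| D4 | 1 (D7) | 0 | next infusion, premedicated and slowed |
| D7 | 0 | 0 | no scheduled dose to which it could apply |

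4. *Could the next-infusion text be meant for Part A?* No. Part A is a single infusion (4.3), so a later scheduled infusion exists only in Part B, where 4.9 forbids it after a DLT.
5. *Could it mean the restarted remainder of the same infusion?* That is hard to sustain. Section 10.5 has separate wording for that situation ("Following the completion or termination of a restarted infusion due to an IRR"), and its premedication requirement is directed at future infusions.
6. *Does 10.5 yield to 4.9?* Not in its text. Its opening says "the following treatment recommendations are provided and may be modified per local treatment standards and guidelines as appropriate", which defers to local standards only.

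**Where the conflict does not arise:** Part A; D7; Grade 4 reactions (10.5 discontinues); Grade 3 reactions unresolved at 6 hours (10.5 discontinues); reactions assessed None or Remote (not DLTs).

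**Count of infusions** (inputs from Protocol 12.1 and 4.3: 18 active and 6 placebo patients, 3 infusions each):

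- Active infusions planned in Part B: 18 × 3 = 54.
- Active infusions on D1 and D4: 18 × 2 = 36.
- Placebo infusions on D1 and D4: 6 × 2 = 12, so 36 + 12 = 48 in all.

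Relatedness is judged under the blind (11.2.1), so the textual conflict could also arise for a placebo patient. Re-exposure to KAN-101 could not. The relevant ceiling is therefore 36 of 54.

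**The case against.** The strongest reply is that a site can comply with both sections. Section 4.9 is absolute. Section 10.5 never orders a further dose: it sets conditions for one if it is given, calls its content recommendations, and keeps some use for Grade 3 reactions judged unrelated. A site that obeys Section 4.9 never reaches the next-infusion text. Redosing would also have to get past the study pause and the SMC review, and the SAP names Section 4.9 as the governing rule.

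Much of this stands. It shows which rule is probably intended and makes redosing less likely. It does not settle the matter, for four reasons:

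- The latitude in Section 10.5 is tied to local treatment standards, and its Grade 3 premedication text is worded as a requirement.
- Section 10.5 does not limit its future-infusion instructions to unrelated reactions.
- Section 4.6 states a study pause, but Section 4.9 and the synopsis word much of it around enrollment and treating additional patients, which does not plainly address the affected patient's own next dose. The synopsis does not repeat the patient-level bar, and the discontinuation reasons in Section 4.10 do not name DLTs.
- The SAP does not instruct a site that is managing a reaction.

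A reader might also infer that the remainder of an interrupted dose is left unregulated. The documents do not support that as a separate fault: Section 10.5 withholds the remainder if the reaction is unresolved at 6 hours and refers to restarted infusions, which implies that a resolved reaction permits a restart. Nor do the alternative slower rates for the next infusion bear on this point; both are slower than the planned 30 minutes.

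**Conclusion.** The conflict is real and narrow, and it should be fixed. It concerns a Grade 3 infusion reaction in Part B, on D1 or D4, assessed as Possible, Probable or Definite, that resolves within 6 hours. Section 4.9 then allows no further scheduled dose, while Section 10.5 describes how to give the next one and does not defer.

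Re-exposure to drug could follow at most 36 of the 54 planned active infusions. That is a count of opportunities. The documents give no rate for such reactions, so no expected number of affected patients is claimed.

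Two stronger readings should be avoided. Section 10.5 does not compel redosing, and the safeguards above make it unlikely. Escalation is not compromised either: the reaction counts as a DLT whichever section the site follows, so DLT counts and the NTD rule are unaffected.

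The conclusion assumes that the patient-level bar in Section 4.9 is the intended rule, which SAP 3.1 supports.

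**What to change.** Add a short statement to the Grade 3 item of Section 10.5, with a matching reference in Section 10.2, to this effect:

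- A Grade 3 infusion reaction assessed as related to KAN-101 is a DLT under Section 4.6.
- In Part B, Section 4.9 then applies and the patient receives no further scheduled doses.
- The instructions for future infusions apply only to reactions assessed as not drug related (None or Remote).

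Keep the rule that discontinues treatment at a second reaction of Grade 3 or above.

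**Cost:** a short protocol amendment, its submission to the IRB/IEC (Protocol 13.4) and a memo to sites. No extra patients, visits or procedures are needed, and the analysis does not change.

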4.10. Treatment Discontinuation

Patients will be discontinued from treatment for any of the following reasons:

- An AE that requires permanent discontinuation of study treatment*
- Noncompliance with the protocol
- Investigator decision
- Patient becomes pregnant

- Patient death
- Patient lost to follow-up
- Termination of the study by the Sponsor
- Voluntary withdrawal of consent by patient

**AEs leading to the discontinuation of KAN-101 will be followed until resolution, resolution to baseline, or until the event is considered stable or chronic.*

The reason for treatment discontinuation will be documented.

All patients will have a final Follow-Up approximately 20 days (D21±1) after the single dose of KAN-101 in Part A and approximately 20 days (D28±3) after the third and final dose in Part B, unless the patient withdraws from the study prematurely ([Section 4.10](#)).

4.11. Study Withdrawal

Patients may voluntarily withdraw from the study at any time for any reason without prejudice.

Patients will be withdrawn from the study for any of the following reasons:

- Investigator's decision
- Patient death
- Patient lost to follow-up
- Termination of the study by Sponsor
- Voluntary withdrawal of consent by patient

5. STUDY POPULATION

5.1. Inclusion Criteria

1. Adults aged 18 to 70 years inclusive
2. Diagnosed with CeD based on positive serology (eg, tissue transglutaminase IgA antibody [tTG-IgA] and/or deamidated gliadin peptide IgG [DGP-IgG]) and intestinal histology consistent with \geq Marsh Type II or with evidence of villous atrophy
3. Has HLA-DQ2.5 genotype (*HLA-DQA1*05* and *HLA-DQB1*02*) (homozygotes or heterozygotes)
4. Has followed a GFD for > 12 months immediately prior to study entry
5. Negative or weak positive for tTG IgA and negative or weak positive for DGP-IgA/IgG during screening
6. Male or female. Females of childbearing potential must use at least 2 acceptable birth control methods
7. Capable of understanding and complying with protocol requirements
8. Patient understands and has signed the informed consent form (ICF)

5.2. Exclusion Criteria

1. Refractory CeD
2. Selective IgA deficiency
3. Positive for HLA-DQ8 (*DQA1*03*, *DQB1*0302*)
4. Previous treatment with tolerance-inducing therapies for CeD
5. Known wheat allergy
6. **Part B only:** History of hyperacute (requiring medical treatment) or prolonged symptoms (> 48 hours) following gluten exposure
7. Has active inflammatory bowel disease (eg, Crohn's disease, colitis)
8. Presence of other autoimmune disorders in addition to CeD, including but not limited to type 1 diabetes, rheumatoid arthritis, psoriasis, autoimmune thyroid disease, etc.
9. Uncontrolled or significant medical conditions (including active infections or chronic hepatitis) which, in the opinion of the Investigator, preclude participation
10. Patients with clinical signs and symptoms consistent with COVID-19 (eg, fever, dry cough, dyspnea, sore throat, and fatigue) or confirmed infection by appropriate laboratory test within the last 4 weeks prior to screening or on admission

Note: Patients who experienced symptoms consistent with COVID-19 or confirmed infection during the screening period (ie, after signing the ICF but before dosing) may be rescreened after 4 weeks

11. Patients with a prior severe course of COVID-19 requiring extracorporeal membrane oxygenation (ECMO) or mechanical ventilation
12. Receipt of chronic, systemic non-biologic immunosuppressive or immunomodulatory therapies within the last 3 months (eg, methotrexate, sulfasalazine, or corticosteroids such as prednisone, etc.)
13. Positive for HIV, HBV, or HCV
14. Receipt of any vaccination within 4 weeks prior to first dose of study drug
15. Receipt of biologic immunosuppressive or immunomodulatory therapies within the last 12 months (eg, adalimumab, etanercept, certolizumab, etc.)
16. Has any of the following laboratory parameters at Screening:
 - a. Hemoglobin < 10 g/dL
 - b. Platelet (PLT) count < $100 \times 10^9/L$
 - c. White blood cell count (WBC) outside the normal range and assessed as clinically significant by the Investigator
 - d. Alanine aminotransferase (ALT), aspartate aminotransferase (AST), or alkaline phosphatase (ALP) > 1.5 x the upper limit of normal (ULN)
 - e. Estimated glomerular filtration rate (eGFR) $\leq 60 \text{ mL/min/1.73 m}^2$ based on the Cockcroft-Gault equation during screening
17. Average alcohol consumption of > 2 drink-equivalents per day
18. History of dermatitis herpetiformis
19. Pregnant or breastfeeding

6. STUDY PROCEDURES AND ASSESSMENTS

Time points for assessments collected throughout the study can be found in the Schedule of Assessments ([Table 1](#) and [Table 2](#)). A brief description of each assessment can be found below.

6.1. Screening and Treatment Procedures and Assessments

6.1.1. Informed Consent

An ICF must be signed by prospective patients prior to initiating any study-specific procedures. Standard of care assessments performed prior to ICF signing may fulfill study eligibility requirements if performed within the screening period.

6.1.2. Inclusion and Exclusion Criteria

Inclusion and exclusion criteria ([Section 5](#)) will be reviewed for each potential patient. Eligibility will be documented in the electronic case report form (eCRF).

6.1.3. Medical History, Demographics, and Celiac Disease History

Complete medical history will be obtained, including demographics, symptoms at diagnosis, disease history, and length of time on a GFD.

6.1.4. Concomitant Medications and Procedures

At screening, concomitant medications will be recorded. Assessment of any change in concomitant medications, or procedures since the last visit will occur at all further patient visits through the final Follow-Up Visit.

6.1.5. Incidental Gluten Exposure Assessment

Assessment of any incidental gluten exposure will be captured at all study visits.

6.1.6. Physical Examination and Vital Signs

A full physical examination (PE) and vital signs check will be performed at the time points specified in the Schedule of Assessments ([Table 1](#) and [Table 2](#)). PEs will also be conducted as clinically indicated.

The PE will include an assessment of general appearance, skin, head, neck, throat, lymph nodes, cardiovascular, neurological, thyroid, musculoskeletal/extremities, respiratory, abdomen, height, and weight (baseline only). Vital signs will include temperature, pulse rate and blood pressure (BP) (sitting for 5 minutes). If vital signs need to be repeated during a single visit, assessments should be conducted approximately 5 minutes apart.

Any new CS abnormality from baseline should be recorded as an AE.

6.1.7. Electrocardiogram

All electrocardiograms (ECGs) will be standard resting 12-lead ECGs performed after the patient has been supine for at least 5 minutes. Patients will be instructed to remain completely

stationary (no talking, deep breathing, sleeping or swallowing) for approximately 10 seconds during the ECG recording. When possible, serial reads on dosing days should be performed by leaving the ECG electrode pads in place for subsequent assessments to ensure comparable ECG reads. While ECGs are being acquired, patients and staff are prohibited from having devices (cell phones, fans, heaters and other radiofrequency signals) that emit electrical interference in the room. If the initial ECG at a timepoint is abnormal then the ECG should be repeated 2 additional times (approximately 2 min apart) within 15 min of the initial ECG.

When an ECG is scheduled at the same time of a blood collection, the ECG will be obtained prior to the blood collection. ECG occurring near meals will take place prior to meals.

All study ECGs will be evaluated by the site Investigator or qualified designee (“local reader”) and interpreted for safety. The local reader will provide global interpretation of normal, abnormal and not clinically significant, abnormal and clinically significant, or unable to evaluate. Additionally, ECGs will be transmitted electronically to a central ECG core lab for cardiologist over read.

ECGs will be conducted as outlined in [Table 1](#) and [Table 2](#). The local reader will review the screening ECG to confirm eligibility. For rescreening, the ECG only needs to be repeated if >3 months have elapsed from last assessment.

